5.2 Interim Analyses

Primary Endpoint report should include all enrolled 72 subjects in 1 month data as the enrollment could not be completed as plan of all the subjects. The BSC study team internally decided to add an interim analysis to care about the subject's safety, not only include Primary Endpoint and show all data that includes 6 month and 12 month in the PE report.

5.3 Subgroup Analyses

Primary endpoints and/or additional assessments will be summarized by the following categories (but not limit to):

- Lesion location (distal, mid, proximal, ostial)
- Sex (male, female)
- Age (-64, 65-74, 75-)
- Lesion Characteristics (lesion length -50, 50-100, 100-150, 150- mm)
- Jetstream Catheter size (SC1.6, SC1.85, XC 2.1/3.0, XC 2.4/3.4)
- Diabetes (medically treated, non-medically treated)

All subgroup analyses are observational. No formal tests of hypotheses are proposed for subgroups and therefore alpha-adjustment for multiple comparisons will not be used.

5.4 Missing Data, Drop-Outs, and Protocol Deviations Handling

Boston Scientific will employ robust oversight in order to minimize the loss of subjects throughout any trial follow-up. Additionally, the case report forms are easy-to-follow and maximize the data collection required at each follow-up visit without placing undue burden on the subject. Strategies that are planned to be utilized in the study include:

- Ensure that site personnel are properly trained on the data that is required to be collected and the importance of planning for the follow-up visits.
- Tools in the site's Manual of Operations to assist with follow-up visit planning (e.g. follow-up wheels or similar tools).
- The use of trial newsletters to remind sites of upcoming visits and other project-related milestones to ensure data is being entered promptly and is complete.

5.5 Sensitivity Analysis for Missing Outcome Data

Sensitivity analyses for the primary effectiveness and/or safety endpoints assessment will be conducted to assess the impact of missing data on the result's robustness. In addition to the use of the worst-case analysis, the tipping point analysis will be performed as post-hoc analysis to consider all combinations of present/absent for all subjects with missing primary outcome.

The analysis finds a (tipping) point in this spectrum of assumptions, at which conclusions change from being favorable to the experimental treatment to being unfavorable. After such a tipping point is determined, clinical judgment can be applied as to the plausibility of the assumptions underlying this tipping point. The tipping point can be identified while the result is no longer statistically significant. This imputation analysis used a specified

sequence of shift parameters, which adjust the imputed values for observations in the active treatment group. The tipping point can be identified while the result is no longer statistically significant. A sample of SAS code for sensitivity analysis using the tipping-point method is provided below.

Multiple imputation often assumes that missing values are missing at random (MAR), and the following statements use the MI procedure to impute missing values under this assumption:

```
proc mi data=Mono2 seed=14823 out=outmi;
  class Trt;
  monotone reg;
  var Trt y0 y1;
run;
```

The following statements generate regression coefficients for each of the 25 imputed data sets:

```
ods select none;
proc reg data=outmi;
  model y1= Trt y0;
  by Imputation;
  ods output parameterestimates=regparms;
run;
ods select all;
```

The following statements combine the 20 sets of regression coefficients:

```
proc mianalyze parms=regparms;
  modeleffects Trt;
run;
```

The "Parameter Estimates" table will be created which displays a combined estimate and standard error for the regression coefficient for Trt. The table displays a 95% confidence interval, which does not contain 0. The table also shows a t statistic of with the associated p-value 0.0011 for the test that the regression coefficient is equal to 0.

The conclusion is usually based on the MAR assumption.

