### **7.2.1. *Treatment and Control***

Subjects enrolled in this clinical trial will not be randomized, and there is no control group in this study. All eligible subjects will receive treatment with the Jetstream System.

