3.1.2 Safety Hypotheses

The primary safety hypothesis to be tested is that 30-day MAE-free rate in subjects treated with Jetstream meets the PG at a one-sided significance level of 2.5%.

The null hypothesis (H_0) states that the PG is not met as opposed to the alternative hypothesis (H_1) which states that the PG is met. The hypotheses inequalities are shown below:

$$H_0: Pt \leq PG \text{ (not met)}$$

$$H_1: Pt > PG \text{ (met)}$$

where Pt is the 30-day MAE-free rate for the subjects treated with Jetstream System and the PG is 88%. The PG of 88% is estimated on the basis of available literature and is consistent with those described atherectomy outcomes

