3.1.3 Safety Sample Size

The overall sample size is consist of the primary cohort and roll-in subjects. The primary cohort is driven by the primary safety endpoint. Approximately 72 subjects are planned to be enrolled in the single-arm study. The sample size justification is based on the following assumptions.

- Power $\geq 90\%$
- One-sided significance level (alpha) = 2.5%
- PG for 30-day MAE-free rate = 88%
- Expected 30-day MAE-free rate = 99%
- Attrition rate in 30 days = 15%
- N = 50 evaluable subjects are required at 30 days
- A maximum of N = 60 subjects to be enrolled in the primary cohort at baseline
- With additional 2 roll-in subjects per site, the overall subjects to be enrolled are approximately 72.

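### The sample SAS code in SAP 5.5 does not carry out the tipping-point analysis that the section describes, and its target coefficient cannot be estimated in a single-arm trial

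*SAP*

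**What the plan says.** Protocol 7.2.1 states that "there is no control group in this study". The two primary tests are one-sample tests. Safety compares a proportion with a fixed goal ("where Pt is the 30-day MAE-free rate for the subjects treated with Jetstream System and the PG is 88" per cent, SAP 3.1.2), and effectiveness is a paired t-test on the change in %DS (SAP 3.2.4).

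For missing outcomes, Protocol 11.3.8 gives one sentence, and Protocol 11 leaves analysis detail to the SAP. SAP 5.5 then says three things in prose:

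- Sensitivity analyses will cover effectiveness and/or safety.
- Besides a worst-case analysis, a tipping-point analysis, labelled post-hoc, will run through every event/no-event assignment for subjects with a missing primary outcome.
- Imputed values will be moved by a sequence of shift parameters. No values, range or step are given.

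The sample code has three steps: PROC MI on Trt, y0 and y1 with a monotone regression method; PROC REG with "model y1= Trt y0"; and PROC MIANALYZE on Trt alone. The text around it reads "The following statements generate regression coefficients for each of the 25 imputed data sets" and then "The following statements combine the 20 sets of regression coefficients". It goes on to report a confidence interval that excludes zero and an "associated p-value 0.0011 for the test that the regression coefficient is equal to 0". It closes on the missing-at-random assumption.

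**The concern.** The code and the prose describe different analyses. A tipping-point analysis departs step by step from missing-at-random until the conclusion changes. The code never departs from it. It also estimates a between-arm difference, which this trial does not have, rather than an MAE-free rate or a mean %DS reduction. A programmer who follows the code would not produce the analysis that the prose describes.

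Nothing else in the plan fills the gap. SAP 5.4 lists retention measures only. The worst-case sections, SAP 3.1.5 and 3.2.5, give the minimum results needed for success, not a rule for filling in missing outcomes. SAP 5.10.2 limits the safety denominator to subjects who reach day 23 or have an event, so the main safety result is in effect a complete-case result, although SAP 4.1 defines ITT as all enrolled subjects. Section 5.5 is therefore where the effect of missing safety data would be examined. It matters because the safety test tolerates very few events, and under SAP 3.3 effectiveness is tested only if safety is met.

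**Working it through.** **Inputs.** Goal 88% (SAP 3.1.2); "One-sided significance level (alpha) = 2.5" per cent (SAP 3.1.3); 60 enrolled in the primary cohort, 50 evaluable needed and 15% attrition at 30 days (SAP 3.1.3; Protocol 9.3 calls 15% a maximum); mean %DS reduction 40, SD 18 (SAP 3.2.3). Missing at the planned maximum: 60 × 0.15 = 9, leaving 51.

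**1. Reproduce the SAP's own example (SAP 7.3).** z = (x/n − 0.88) / √(0.88 × 0.12 / n). For 49/50: 0.10 / 0.04596 = 2.176, one-sided p = 0.0148, exact lower limit 0.8935. All agree with the printed output. For 48/50, z = 1.741 and p = 0.0409, a fail, consistent with the limit of one MAE in 50 in SAP 3.1.5.

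**2. Can the code estimate its target?** With one arm, Trt takes a single value, so its column is a multiple of the intercept column. The matrix [1, Trt, y0] has rank 2 for 3 columns. Only the combined intercept-plus-Trt term is determined. The Trt coefficient, the one quantity pooled, is not.

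**3. Safety tipping count by enumeration.** Each row gives total MAEs among 60, observed plus missing counted as MAE. The Wald bound is p̂ − 1.96√(p̂(1 − p̂)/60).

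| MAEs | MAE-free | z | one-sided p | exact lower | Wald lower |
|---|---|---|---|---|---|
| 0 | 60/60 | 2.860 | 0.0021 | 0.9404 | 1.0000 |
| 1 | 59/60 | 2.463 | 0.0069 | 0.9106 | 0.9509 |
| 2 | 58/60 | 2.066 | 0.0194 | 0.8847 | 0.9212 |
| 3 | 57/60 | 1.669 | 0.0476 | 0.8608 | 0.8949 |
| 4 | 56/60 | 1.271 | 0.1018 | 0.8380 | 0.8702 |
| 9 | 51/60 | −0.715 | 0.7627 | 0.7343 | 0.7596 |

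The z test and the exact bound both pass with 2 MAEs and fail with 3. So the result tips at 3 of the 9 missing if none is observed, and at 2 if one is observed. The Wald bound passes with 3 and fails with 4, giving tipping counts of 4 and 3. The complete-case z values on 51 subjects are 2.637 with no MAE and 2.206 with one, so both cases would first have been declared a success. If all 9 missing count as MAE, safety fails even with none observed.

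**4. Effectiveness.** Take 51 observed reductions (mean 40, SD 18) and set 9 missing reductions to 0. Mean = 51 × 40 / 60 = 34.0. Sum of squares = 50 × 18² + 51 × 6² + 9 × 34² = 16,200 + 1,836 + 10,404 = 28,440, so SD = √(28,440/59) = 21.96 and t = 34.0 / (21.96/√60) = 12.0. With multiple imputation and a downward shift, the pooled t is 10.8 at a shift of 40 points, 2.36 at 150 and 1.75 at 170, so the result tips near 160 points. That is outside the possible range: from a baseline of 70% stenosis the worst change is 70 − 100 = −30, and setting all 9 to −30 still gives t = 7.58.

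**The case against.** The strongest reply is that the code is only a sample. The CRO writes and validates the programs (SAP 6 and 7), the prose of 5.5 governs, and no success criterion in SAP 3.3 uses this analysis. Much of that stands. The prose enumeration needs no Trt variable, runs in one arm and suits a binary endpoint. A reader might infer from the code that the plan contains no robustness check at all, or none that could give an answer for either endpoint. The documents do not support that: for safety, the method in prose is well defined.

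Four other readings also go too far:

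- That the program would fail to run. What is shown is that the Trt effect is not identified; how SAS would behave was not tested.
- That the code was taken from another data set. The 25/20 mismatch and the ready-made p-value suggest it, but the documents name no source.
- That a continuous y0/y1 model is wrong throughout. With Trt removed it could serve baseline and post-atherectomy %DS; the mismatch is with MAE status.
- That missing data threaten both endpoints. The 15% is loss to follow-up at 30 days, whereas %DS is measured during the procedure, and step 4 shows that effectiveness is robust.

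What the reply does not answer is that the section presents this code as the tipping-point method, and a CRO is expected to work from it.

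**Conclusion.** The concern holds as a defect in the specification. The code in SAP 5.5 does not implement the analysis that the section describes, addresses neither primary test, and pools a coefficient that one arm cannot supply. The prose commitment for safety is usable but is contradicted by the code, weakened by the post-hoc label and hedged by and/or. For %DS, shifts are mentioned without any usable specification. No fill-in rule is given for the worst case.

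The practical weight is on safety: at the planned maximum attrition, 2 or 3 adverse assignments among 9 missing subjects reverse the result (3 or 4 under Wald). These counts assume 60 enrolled, exactly 9 missing and 0 or 1 observed MAE. The lower pair rests on the null-variance z test of SAP 7.3 or the exact bound. SAP 3.3.1 names no method for its confidence bound and SAP 7.3 prints both Wald and exact limits, so the choice must be stated. Nine missing is a planning ceiling, not a forecast; fewer missing subjects would leave less to decide. This should be corrected before analysis.

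**What to change.** Replace the code and the text around it in SAP 5.5.

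- **Safety.** For k = 0 to m, where m is the number of enrolled primary-cohort subjects with missing 30-day MAE status, count k as MAE and rerun the 88% comparison on all enrolled primary-cohort subjects, using the same test or bound as the primary analysis. Report the smallest k that fails. Define k = m as the worst case.
- **Effectiveness.** Impute post-atherectomy %DS from baseline %DS, without Trt. Add a worsening shift in fixed, stated steps up to no reduction. Report whether, and at what shift, the lower bound reaches zero.
- **Wording.** Apply this to both primary endpoints rather than and/or, call it pre-specified, and delete the 25/20 text, the confidence-interval statement and the 0.0011 p-value.

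The cost is a SAP amendment and a short program. No extra subjects or data are needed, and SAP 5.16 already provides for amendment before the primary analysis.

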5.6 Multivariable Analyses

Univariate and multivariable analyses will be performed as post-hoc analyses to assess the effect of potential predictors for the primary safety endpoint in a logistic regression model.

Clinically and/or statistical meaningful baseline covariates will be selected in the regression model.

For each outcome, predictors will be listed in ascending order of p-value. Univariate analyses will be performed. For the multivariable analyses, only coefficients in the final model, i.e., with p-values less than 0.1 will be listed.

No formal conclusion will be made by this secondary post-hoc analysis.

An appropriate regression model will be used to assess the effect of each individual covariate on study outcomes. Those variables found to be significant at the 0.1 level will be included in a multivariable regression model. The significance level thresholds will be set at 0.1.

For each outcome, predictors will be listed in ascending order of p-value. For the multivariable analyses, coefficients with p-values greater than 0.1 will not be listed.

5.7 Angiography

All subjects will undergo angiographic assessment during the index procedure per standard of care. Subjects requiring any subsequent revascularization procedure of the target vessel during the 12-month follow-up period will undergo angiographic assessment at the time of reintervention as standard of care.

Angiographic data and images collected during the index procedure and during any revascularization procedure of the target vessel during the follow-up period must be forwarded to the angiographic core laboratory for analysis. Angiograms performed at outside institutions should also be sent to the core laboratory. Angiograms will be centrally assessed by the core laboratory, for qualitative and quantitative analyses.

5.8 Duplex Ultrasound

Duplex Ultrasound (DUS) assessments will be performed at 6 months (182 ± 30 days) and 12 months (365 ± 30 days) post-index procedure. Only records obtained during the clinical visit window will be selected for analysis unless the Biostatistics personnel are informed otherwise. In the case where multiple examinations are performed during the visit window, the best interpretable record will be selected. Measurements from DUS assessments that occur after a TLR will not be excluded from selection, but rather, endpoint definitions will appropriately account for the presence or absence of a prior TLR. Therefore a prior TLR may suggest a primary patency failure regardless of DUS result(s).

In the determination of $>50\%$ stenosis, a $PSVR > 2.4$ is used for the primary assessment. However a $PSVR > 2.0$ (e.g. alternative definition of vessel patency in SuperNOVA; BMS) and/or $PSVR > 2.5$ (e.g. definition of vessel patency in MAJESTIC; DES) and/or other clinical recommendation may be used in post-hoc analyses for publication purpose

The primary patency (binary rates) will be calculated based on the subjects who have adequate follow-up and/or have DUS assessments. The denominator will be based on number of subjects who reach the protocol-defined lower window and/or have events. The numerator will be based on number of subjects who finish the scheduled assessments (i.e. success or failure) within the protocol-defined upper window.

Follow-up Visit	Protocol Defined Lower ¹ Window for Assessment	Protocol Defined Upper Window for Assessment
6 Months	152	212
12 Months	335	395

¹Days for adequate follow-up

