**Table 4.2-1: Major Adverse Events at 30 Days and 6 Months**

	30 Days (n=172)	6 Months (n=162)
MAE	2 (1.1%)	31 (19%)
TVR	0 (0%)	4 (2.5%)
Death*		
Sudden Cardiac Arrest (probable)	0 (0%)	1 (0.6%)
Amputation	2 (1.1%)	2 (1.2%)
TLR	0 (0%)	25 (15%)
Non-Q wave MI	0 (0%)	1 (0.6%)

At the 6-month follow-up, 31 subjects had at least 1 MAE. The freedom from serious adverse device effects (SADEs) and TLR at 6 months post-procedure, was 85% with a 95% lower confidence interval of 78%.

Success in crossing and debulking the target lesion was achieved in 99% (208/210) of the cases. Thirty-three percent of the cases were atherectomy procedures alone, while in 59% of the lesions, adjunctive low-pressure angioplasty was also employed. Stenting was indicated in 7% of the subjects. Mean diameter stenosis was reduced from  $79.4\% \pm 17.7\%$  at baseline to  $35.0\% \pm 16.1\%$  after atherectomy. After adjunctive therapy, the diameter stenosis was further reduced to  $21.4\% \pm 10.5\%$ . Interventional success, defined as residual stenosis  $\leq 30\%$  by visual estimation, was achieved in 209/210 (99%) lesions.

Clinical success was achieved in 68% (91/133) at 6 months and 70% (75/107) at 12 months, based on improvement in Rutherford classification. Hemodynamic success was achieved in 52% (63/121) subjects at 6 months and in 52% (51/98) at 12 months.

Primary and secondary duplex-documented patency rates at 12 months were 61.8% (76/123 lesions) and 81.3% (100/123 lesions), respectively. Clinically driven TLR rates were 15% (25/172) at 6 months and 26% (42/162) at 12 months, while TVR rates (including TLR) were 17% (29/172) and 30% (49/162), at 6 and 12 months respectively.

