5.9.1 Kaplan-Meier for Primary Patency

The Kaplan-Meier analysis is aimed to capture the first event for each subject. There are two ways to determine the first event, whichever comes first.

- Clinically-driven TLR date by CEC
- Ultrasound date to identify a subject not patent (i.e. PSVR>2.4)

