7.1 Derivation for Primary Patency

The primary patency is based on PSVR measurement derived from the core laboratory data provided by Vascular Ultrasound Core Lab (i.e. VASCORE), clinically driven TLR determined by CEC form, and bypass surgery determined in the text field by AE form.

A subject's 12-month primary patency is derived as patent (i.e. "YES") only if:

- VASCORE form: a subject's 12-month DUS assessment is done and PSVR ≤ 2.4 ; and
- CEC form: no clinically-driven TLR prior to 12-month DUS visit. Note that if there is one clinically-driven TLR and the event date is later than ($>$) 12-month DUS visit, the subject's primary patency will remain "YES"; and
- AE form: no bypass surgery is identified prior to 12-month DUS visit. Note that if there is one surgery and the surgery date is later than ($>$) 12-month DUS visit, the subject's primary patency will remain "YES".

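### SAP 5.8 admits subjects to the patency denominator by days of follow-up, not by having an interpretable scan, so the reported rate depends on scan completion

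*SAP*

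**What the plan says.** SAP 5.8 describes the binary patency rate in three consecutive sentences.

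- Population: "The primary patency (binary rates) will be calculated based on the subjects who have adequate follow-up and/or have DUS assessments".
- Denominator: "The denominator will be based on number of subjects who reach the protocol-defined lower window and/or have events". The table beneath gives lower bounds of 152 and 335 days, and its footnote equates them with adequate follow-up.
- Numerator: "The numerator will be based on number of subjects who finish the scheduled assessments (i.e. success or failure) within the protocol-defined upper window".

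On which scans to use, the same section says: "Only records obtained during the clinical visit window will be selected for analysis unless the Biostatistics personnel are informed otherwise".

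SAP 7.1 classes a subject as patent at 12 months only if the subject's "12-month DUS assessment is done and PSVR" is at or below 2.4, with no clinically-driven TLR and no bypass before that scan. It does not say whether a subject without a scan is NO or missing, and it gives no rule for 6 months.

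The Kaplan-Meier version in SAP 5.9.1 recognises two failures: a clinically-driven TLR, and "Ultrasound date to identify a subject not patent".

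SAP 5.4 covers only the prevention of data loss. SAP 5.5 covers missing data for the primary endpoints only. Neither gives a rule for a missing DUS.

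**The concern.** SAP 5.10.1 and 5.10.2 use the same denominator rule for MAE rates, where it makes sense: a subject followed to the window with no reported event is informative. Patency is different. Protocol 6.2.2 defines it by the DUS velocity ratio, so follow-up without a scan says nothing about the vessel.

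With this denominator, the published 6- and 12-month patency would move with the proportion of scans obtained as well as with the state of the vessels. It could also differ from the Kaplan-Meier estimate for the same reason, because a missing scan is not a failure there.

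The exception for out-of-window scans adds a second uncertainty. No criterion, decision-maker or timing is given for letting such scans in.

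**Working it through.** **Inputs**

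- Visit windows: "6 months (182 ± 30 days) and 12 months (365 ± 30 days) post-index procedure" (SAP 5.8).
- Cohort: 60 subjects, the planned primary cohort (Protocol 11.1.1.2), all taken to reach the window.
- Patency among scanned subjects: 61.8%, from 76/123 in Protocol 4.2.1. It is borrowed only as a plausible level. It is a per-lesion figure for the first-generation device. A level of 80% is also run, as an assumption.
- Share without an interpretable scan: 5%, 10%, 15% and 20%. This is an assumption, because the documents give no such rate. The 15% in the sample-size section is loss to follow-up at 30 days.

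**The plan's own figures.** 182 − 30 = 152 and 182 + 30 = 212; 365 − 30 = 335 and 365 + 30 = 395. These match the table in SAP 5.8.

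**Three readings.** Let N = 60, let S be the subjects scanned, and let P be the patent subjects (61.8% of S, rounded to whole subjects). Scans are taken to be missing regardless of vessel status, and all failures are taken to be found on a scan.

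- Literal 5.8: (success + failure) / reached window = S/N.
- 7.1 numerator over 5.8 denominator: P/N.
- 7.1 numerator over a scan-based denominator: P/S.

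| Missing | S | P | S/N | P/N | P/S |
|---|---|---|---|---|---|
| 0 (0%) | 60 | 37 | 100% | 61.7% | 61.7% |
| 3 (5%) | 57 | 35 | 95% | 58.3% | 61.4% |
| 6 (10%) | 54 | 33 | 90% | 55.0% | 61.1% |
| 9 (15%) | 51 | 32 | 85% | 53.3% | 62.7% |
| 12 (20%) | 48 | 30 | 80% | 50.0% | 62.5% |

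The small movement in P/S comes from rounding to whole subjects.

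At 80% patency among those scanned, P/N is 76.7%, 71.7%, 68.3% and 63.3% for 5%, 10%, 15% and 20% missing, while P/S stays between 79% and 81%.

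**Reading the table.** S/N does not contain P, so it is the same whether every scanned vessel is open or every one is closed. P/N falls by 2/60 = 3.3 points at 5% missing for both levels. At 20% missing it falls by 7/60 = 11.7 points at the 61.8% level and by 10/60 = 16.7 points at the 80% level.

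**The case against.** A reader might infer that the SAP scores a missing scan as lost patency. No sentence says so. The effect arises only when the 5.8 denominator is joined to the 7.1 rule for YES, and 7.1 covers 12 months only. Under the literal 5.8 numerator a failing scan is counted and a missing one is not, so the two are treated differently. The population sentence is also loose enough that someone could read it as limited to scanned subjects. All of this stands. It does not rescue the denominator: correcting the numerator alone produces P/N, and no other section supplies a rule for a missing DUS.

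A reader might also divide the predecessor study's 76 patent lesions by the 162 in its 12-month TLR denominator to show the size of the effect. The documents do not support that.

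- It divides lesions by subjects, and that study had 210 lesions in 172 subjects.
- Table 4.2-1 uses 162 as the 6-month number, and the diabetes re-analysis in the same section gives 12-month TLR as 16/80 + 26/92 = 42/172.
- Only 107 subjects had 12-month Rutherford data and 98 had hemodynamic data, so the gap between 123 and 162 cannot be read as missing scans among followed subjects.

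It is tempting to accept a late patent scan, since a vessel open after day 395 was presumably open at day 365. Accepting late patent scans while dropping late failing ones biases the rate upward. With 100 subjects, 62% patent and 10% scanned late (all assumed), 3.8 failing subjects drop out and the rate becomes 62/96.2 = 64.4%.

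On the discretionary clause, the SAP does not say that decisions will follow sight of results. DUS reading is a blinded core-laboratory assessment (Protocol 12.3), and changes to planned analyses must be documented (SAP 5.16). The clause is still undefined.

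Fixed ±30-day windows are a normal choice, and missing-as-failure is a recognised conservative convention. Either is acceptable if stated.

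**Conclusion.** The point holds as a defect in how the patency proportion is defined. The stated denominator does not require a scan, the stated numerator counts completed assessments, and missing DUS has no rule. Taken literally, the figure is a scan-completion rate. With the numerator corrected to the 7.1 classification, reported patency is understated by roughly 3 to 17 points over the range examined.

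That size rests on an assumed 5% to 20% of scans missing, on missingness unrelated to patency, and on assumed patency levels of 61.8% and 80%. The 6-month case further assumes that 7.1 is extended to that visit.

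The divergence from Kaplan-Meier follows from the failure events listed in SAP 5.9.1. A reader might go further and say that the curve censors unscanned subjects, but that section states no censoring rule.

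The consequence is limited. SAP 5.1 plans no hypothesis test for patency, no comparison with the predecessor's patency rate is planned, and neither primary endpoint is touched.

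**What to change.** Amend SAP 5.8 and 7.1 together, for both 6 and 12 months:

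1. Numerator: subjects classed as patent for that visit.
2. Denominator: subjects with an interpretable DUS for that visit, plus subjects with an earlier patency failure (clinically-driven TLR or bypass). Keeping the second group matters because Protocol Table 10.1-1, note b, requires no scan after bypass of the target lesion.
3. State that a subject with neither is missing, and report how many there are at each visit.
4. Show missing-as-failure as a sensitivity analysis.
5. Replace the exception for out-of-window scans with a fixed rule that treats patent and failing scans alike, for example excluding both from the main analysis and including both in a sensitivity analysis.

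The cost is SAP wording only, using data already being collected. The downside is a smaller denominator and reliance on scans being missing for reasons unrelated to patency. Also, earlier failures stay in without a scan while other subjects need one, so the rate will lean slightly low if many scans are missing. The reported count of unscanned subjects lets the reader judge this.
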